## PROTOCOL SYNOPSIS

FULL STUDY TITLE	The Tolerability of Buspirone for Treatment of Anxiety in Parkinson's Disease
CLINICAL PHASE	Phase II
INVESTIGATORS/ STUDY GROUP	[name] (PI), [name] (Co-PI)
STUDY OBJECTIVE	The primary objective of this study is to determine the tolerability of buspirone for the treatment of anxiety in PD.
STUDY RATIONALE	Anxiety is highly prevalent in Parkinson's disease (PD) and negatively impacts quality of life yet it frequently remains untreated and there have been no clinical trials dedicated to evaluating the pharmacological treatment of anxiety in PD. Buspirone, which primarily acts as a 5HT1A receptor partial agonist, is effective for the treatment of generalized anxiety disorder in the general and elderly population. It is not known if it is effective for the treatment of anxiety in the PD population where there is a more heterogeneous phenomenology of anxiety. Buspirone also may diminish levodopa-induced dyskinesias. However, concerns have been raised about its potential to worsen motor function. A tolerability assessment is necessary prior to proceeding with a phase III efficacy trial.
STUDY SITES	University of Rochester
STUDY PERIOD	3 years
STUDY POPULATION AND NUMBER OF SUBJECTS	35 participants with idiopathic PD and clinically significant anxiety as defined by a score of $\geq 14$ on the self-rated Parkinson Anxiety Scale.
STUDY DESIGN	This is a single-center, placebo-controlled, double-blind design with participants randomized with a 4:1 allocation ratio to flexible dosage buspirone (maximum dosage 30 mg twice daily) or placebo for 12 weeks.
MAIN INCLUSION/ EXCLUSION CRITERIA	
Inclusion Criteria:
 
 
1. Diagnosis of idiopathic PD (UK PD Society Brain Bank Diagnostic Criteria)
 
2. Significant anxiety Parkinson Anxiety Scale (<math>\geq 14</math>)
 
3. Able to provide written informed consent
 
4. At least 18 years of age
 
 
Main Exclusion Criteria:
 
 
1. Diagnosis of atypical or secondary parkinsonism
 
2. Concomitant treatment with an MAO inhibitor
 
3. Significant renal or hepatic impairment
 
4. Significant cognitive impairment ( MOCA score <math>< 23</math>)
 
5. Depression with suicidal or homicidal ideation and concern for patient safety based on clinical determination by the investigator
 

DOSAGE: ROUTE AND FORM	Over-encapsulated buspirone tablets or matching placebo administered twice daily by mouth.
DOSAGE: JUSTIFICATION	Participants will initiate treatment with either buspirone 7.5 mg or placebo twice daily. Dosage adjustments will be made at the discretion of the investigators at two-week intervals following pre-specified parameters until the optimal dosage has been obtained. The optimal dosage is one that is associated with optimal anxiolytic benefit without intolerable

	adverse events. Investigators will be allowed to decrease or not escalate the dosage in the presence of adverse events. The selected dosage range of 7.5 mg twice daily up to 30 mg twice daily is consistent with current prescribing guidelines.
DURATION OF TREATMENT	12 weeks
PRIMARY OUTCOME MEASURE(S)	The primary outcome measure is the proportion of participants who fail to complete the 12-week study on study drug.
SECONDARY OUTCOME MEASURE(S)	
Safety and Tolerability:
 
 
(1) Number and type of adverse events
 
(2) Number and type of serious adverse events
 
(3) Mean change in MDS-UPDRS motor from baseline to 12 weeks
 
(4) Mean change in calculated levodopa-equivalent dose from baseline to 12 weeks
 
 
Anxiety:
 
 
(1) Mean change in Hamilton Anxiety Rating Scale (HAM-A) from baseline to 12 weeks
 
(2) Proportion of responders (>50% reduction from baseline or reduction to ≤7 on HAM-A) at 12 weeks
 
(3) Proportion “much improved” or “very much improved” on Clinical Global Impressions-Improvement (CGI-I) and Patient Global Impressions-Improvement (PGI-I) at 12 weeks
 
(4) Mean change in Hospital Anxiety and Depression Scale (HADS) from baseline to 12 weeks
 
 
Levodopa-Induced Dyskinesias:
 
 
(1) Mean change in Unified Dyskinesia Rating Scale (UDysRS) from baseline to 12 weeks
 
 
Parkinson Anxiety Scale:
 
 
(1) Correlation of change with CGI-I and PGI-I
 

SAFETY CONSIDERATIONS	Bupirone is FDA-approved for treatment of generalized anxiety disorder. According to the package insert, in premarketing clinical efficacy trials, 10% of 2200 participants discontinued treatment secondary to an adverse event and in pooled analysis of placebo-controlled clinical trials the most common adverse events included dizziness (12%), drowsiness (10%), nausea (8%), headache (6%), nervousness (5%), fatigue (4%), insomnia (3%), lightheadedness (3%), and dry mouth (3%).
SAMPLE SIZE CONSIDERATIONS	A sample size of 21 will provide 80% power to reject the null hypothesis of tolerability (observed intolerability rate of ≤20%) in favor of the alternative hypothesis of intolerability (observed intolerability rate of >20%) if the true intolerability rate is greater than 40%, using a binomial test and a one-tailed significance level of 10%. With the introduction of a placebo arm for blinding and relying on a 4:1 allocation ratio, the sample size increases to 27. The use of a futility design provides a higher probability of correctly failing to reject the null hypothesis of tolerability at the cost of a decreased chance of correctly rejecting the null hypothesis of tolerability. We are willing to accept a higher chance that we declare an intolerable drug tolerable as the expected intolerabilities (headache, nausea, drowsiness, dizziness, and worsening of PD motor function) are not expected to be severe, may be experienced by only a portion of subjects, and could be confirmed in larger studies.

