#### **During the Study:**

- The addition of new anti-parkinsonian medications or increase in dosage of existing anti-parkinsonian medications will be prohibited for the duration of the trial.
- The addition of a new anxiolytic or antidepressant or increase in dosage of an existing anxiolytic or antidepressant will be prohibited for the duration of the trial.
- Participants will not be allowed to initiate or discontinue psychotherapy following enrollment. If they are participating in it at the time of enrollment, it should be continued for the duration of the study.

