## **6.0 CONCOMITANT AND DISALLOWED MEDICATIONS**

### **6.1 Allowed Concomitant Medications**

Enrolling participants may be on PD medications, with the exception of monoamine oxidase inhibitors. The dosage must be stable for 30 days prior to the baseline visit.

No new PD medications may be initiated for the duration of the study and no increases in the dosages of current PD medications will be allowed.

Enrolling participants may be on antidepressants (with the exception of monoamine oxidase inhibitors), antipsychotics, and/or anxiolytics. The dosage must be stable for 30 days prior to the baseline visit and for the duration of the study. The initiation of one of these medications will be prohibited for the duration of the study.

Strong CYP3A4 inhibitors (atazanavir, boceprevir, ceritinib, clarithromycin, cobicistat and cobicistat containing formulations, darunavir, idelalisib, indinavir, itraconazole, ketoconazole, lopinavir, nefazodone, nelfinavir, ombitasvir-paritaprevir-ritonavir, ombitasvir-paritaprevir-ritonavir plus dasabuvir, posaconazole, ritonavir and ritonavir containing formulations, saquinavir, telaprevir, telithromycin, and voriconazole) will be allowed. Participants will be monitored for potential adverse events related to an increase in the serum study drug concentration.

Strong CYP3A4 Inducers (carbamazepine, enzalutamide, fosphenytoin, lumacaftor, mitotaine, phenobarbital, phenytoin, primidone, rifabutin, rifampin, and rifapentine) will be allowed.

Non-dihydropyridine calcium channel blockers (diltiazem, verapamil) and interacting macrolide antibiotics (erythromycin, clarithromycin, and telithromycin) will be allowed. Participants will be monitored for potential adverse events related to an increase in the serum study drug concentration.

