## 6.2 Disallowed Medications and Supplements

The following medications will not be allowed during the study:

- Selective and non-selective MAO inhibitors including those whose primary mechanism of action is not monoamine oxidase inhibition: phenelzine, rasagiline, selegiline, procarbazine, isocarboxazid, tedizolid, tranylcypromine, syrian rue, linezolid, methylene blue, moclobemide
- Initiation of any antidepressants, antipsychotics, or anxiolytics.
- Azelastine
- Conivaptan
- Dapoxetine
- Fusidic Acid
- Idelasib
- Orphenadrine
- Paraldehyde
- Thalidomide
- Grapefruit juice, ginkgo biloba, St. John's wort, and ginseng (which interfere with study drug metabolism).
- Initiation of any new PD medications and increases in the dosage of existing PD medications will be prohibited.
- Participants will also be prohibited from beginning any form of psychotherapy following study entry.

If treatment with a disallowed medication is required, the study drug should be discontinued and the participant should continue in the study off of the study drug. The study drug may be restarted after the disallowed medication is stopped.

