### 13.2 Planned Statistical Analysis

The primary outcome for tolerability is the proportion of participants who fail to complete the 12-week study on study drug, as described in **Sample Size and Accrual**. The number of participants who fail to complete the study on study drug will be determined and if 7 or more participants fail to tolerate the study drug, the null hypothesis will be rejected. Participants who do not complete the study on study drug for any reason will be considered as experiencing intolerability for purposes of the primary analysis.

As a secondary analysis we will calculate the number of participants who fail to complete the study on study drug due to adverse events; separating them from those who fail to complete the study on study drug for alternative reasons. We will also calculate the number of participants who required dosage reductions during the study and use descriptive statistics to describe the average study drug dosage and dosage reductions.

Safety analyses will include tabulating adverse events by treatment group and severity and codifying the relationship to study drug. Serious adverse events attributable to buspirone treatment will be described in detail. Adverse event incidence will be summarized along with the corresponding 95% two-sided confidence interval. The mean change in MDS-UPDRS motor score and from baseline to 12 weeks will be calculated. We will use descriptive statistics to characterize the range and variability of study drug dosages.

Secondary outcomes related to anxiety will include the mean change in HAM-A score from baseline to 12 weeks, mean change in HADS score from baseline to 12 weeks and the proportion of participants "much improved" or "very much improved" on CGI-I, proportion "much improved" or "very much improved" on PGI-I, and proportion of responders ( $> 50\%$  reduction from baseline or reduction to  $\leq 7$  in HAM-A) at 12 weeks. The secondary outcome regarding levodopa-induced dyskinesias will be the mean change in UDysRS score from baseline to 12 weeks. Similar analyses will be done for all outcomes at 2 weeks, 4 weeks, and 8 weeks. For participants lost to follow up, the

last observation carried forward will be used. We will also correlate mean change in the Parkinson Anxiety Scale scores with mean change in the CGI-I and PGI-I scores.

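### Week-12 change in levodopa-equivalent dose cannot rise in participants who stay on study drug and follow the medication rules, so a null result does not show that no extra PD medication was needed; carrying last scores forward is a lesser problem

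*Combined protocol and SAP*

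**What the plan says.** **The outcome.** The synopsis lists, as the fourth safety and tolerability outcome, "Mean change in calculated levodopa-equivalent dose from baseline to 12 weeks". It does not restrict this to participants on study drug.

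**The medication rules.** Three places set the same limit:

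- Section 3.2, in its closing list of rules for enrolled participants: "The addition of new anti-parkinsonian medications or increase in dosage of existing anti-parkinsonian medications will be prohibited for the duration of the trial".
- Section 6.1: "no increases in the dosages of current PD medications will be allowed".
- Section 6.2, in the list of disallowed treatments: "Initiation of any new PD medications and increases in the dosage of existing PD medications will be prohibited".

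None of the three bars a decrease. Section 6.2 continues: "If treatment with a disallowed medication is required, the study drug should be discontinued", with the participant staying in the study off drug. It then adds: "The study drug may be restarted after the disallowed medication is stopped". Sections 8.5 and 8.6 also keep people in follow-up after study drug stops.

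**The analysis.** Section 13.2 counts non-completion on study drug for any reason as intolerability. A secondary analysis counts failures due to adverse events, "separating them from those who fail to complete the study on study drug for alternative reasons". Its safety paragraph names the change in MDS-UPDRS motor score but not levodopa-equivalent dose (LED). The motor sentence reads as if words are missing after a stray conjunction, so LED may have been meant to appear there. For participants lost to follow-up, section 13.2 says the "last observation carried forward will be used". That sentence stands in the paragraph on anxiety and dyskinesia outcomes, so whether it also covers MDS-UPDRS motor or LED is not explicit.

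**The concern.** Section 2.2 names motor worsening as the tolerability worry specific to PD. LED change is a natural companion to the motor score, because a drug that worsens parkinsonism may show itself as a need for more PD medication. Here the medication rules hold that response at zero or below for everyone who stays on study drug within the protocol, whatever the drug does to motor function. A reader of the results could take a null or negative mean as reassurance that the rules alone would have produced.

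The second point is smaller. Study-drug dose is flexible and can be raised every two weeks. For someone lost early, a score carried forward is reported as a week-12 value although it was taken at the dose in force at the last visit.

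**Working it through.** The plan gives no figure for LED change or for the effect of LOCF, so there is none to reproduce. The steps below use the plan's rules and arm sizes.

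**1. What the rules allow**

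| Status at week 12 | PD-medication change possible | LED change |
|---|---|---|
| On study drug, within the rules | none, or a decrease | 0 or negative |
| Off study drug, still followed | increase possible | any sign |
| On study drug, with an increase | protocol deviation | can be positive |
| Temporary increase reversed, study drug restarted, completed on drug | back to the starting regimen | 0 |

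The last row follows from the restart sentence in section 6.2. That person shows no LED change at week 12 and need not count as a primary failure. The documents give no frequency for this sequence.

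**2. Arm sizes.** Section 13.1 needs 21 on buspirone and 27 in all at 4:1. 27 × 4/5 = 21.6 and 27 × 1/5 = 5.4, so about 21–22 and 5–6.

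**3. What the mean would show.** Assumptions, not in the documents: 21 on buspirone; k of them need a rise of L mg/day, stop study drug and stay in follow-up; no one else changes. Arm mean = k × L / 21.

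| k | L = 100 | L = 300 |
|---|---|---|
| 1 | 4.8 | 14.3 |
| 2 | 9.5 | 28.6 |
| 3 | 14.3 | 42.9 |

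Those still on drug average 0. A single 300 mg/day reduction elsewhere cancels three 100 mg/day rises: (3 × 100 − 300)/21 = 0.

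**4. What a count would show.** Clopper–Pearson 95% intervals; for zero events the upper limit is 1 − 0.025^(1/n).

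| Count | Rate | 95% interval |
|---|---|---|
| 1/21 | 4.8% | 0.1% to 23.8% |
| 2/21 | 9.5% | 1.2% to 30.4% |
| 3/21 | 14.3% | 3.0% to 36.3% |
| 0/21 | 0% | up to 16.1% |
| 0/5 (placebo) | 0% | up to 52.2% |
| 0/6 (placebo) | 0% | up to 45.9% |

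If all 35 participants named in the synopsis were randomised (28 and 7), the zero-event limits would be 12.3% and 41.0%. A count is imprecise, but reductions in other people cannot cancel it.

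**5. Dose behind a carried score.** Section 5.1.2 allows one step every two weeks from 7.5 mg twice daily. On the fastest schedule the highest daily dose in force when each score is taken is:

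| Week | 2 | 4 | 6 | 8 | 10 | 12 |
|---|---|---|---|---|---|---|
| Ceiling, mg/day | 15 | 20 | 30 | 40 | 50 | 60 |
| Largest possible gap to week 12 | 45 | 40 | 30 | 20 | 10 | – |

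Weeks 6 and 10 are telephone visits, and of the scales at issue only HAM-A is taken then. The gap is 0 for someone never escalated, and decreases are also allowed. These are limits on dose, not estimates of bias in the scores.

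**6. Precision of per-arm means.** 95% half-width in SD units = t(0.975, n − 1)/√n: 1.24 for n = 5, 1.05 for n = 6 and 0.46 for n = 21.

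**The case against.** The strongest reply is that motor worsening does not depend on LED. MDS-UPDRS motor is scored at baseline, weeks 2, 4, 8 and 12, and at termination and adverse-event visits. The UKU scale covers tremor, rigidity and hypokinesia. Adverse events are tabulated by arm and severity. Needing a barred treatment stops study drug, and not finishing on drug for any reason is a primary failure. Holding PD medication fixed also makes on-drug motor scores easier to read, because extra medication cannot mask worsening. All of this stands. So does the point that the LED mean is not restricted to those on drug, so rises during off-drug follow-up do enter it.

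A reader might therefore infer more than the documents support. They do not show that the LED outcome is empty or that motor worsening would go unseen. LED is one-sided on drug and diluted in the arm mean, while other measures carry most of the signal. What remains is that no planned analysis counts the need for more PD medication, and that a temporary increase followed by restart can be missed by both the week-12 LED change and the primary outcome.

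On LOCF, the termination visit in section 5.2.6 collects HAM-A, HADS, UDysRS, CGI-I, PGI-I and motor scores, so many who withdraw will supply an exit score, though still at the dose reached by then. The outcomes are exploratory and the trial is not powered to compare arms. A reader might infer that LOCF understates the drug's effect, or that it is the main reason on-drug and off-drug values are mixed at week 12. Neither follows: the direction is unknown, and the mix comes mainly from continued follow-up after study drug stops. A repeated-measures model is not free of assumptions either. It relies on data missing at random, which is doubtful if people leave because they cannot tolerate treatment.

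**Conclusion.** The point on LED holds, in limited form. In participants on study drug and within the rules, the change is zero or negative by construction. A rise can enter the arm mean only through off-drug follow-up or a deviation. A null or negative mean is therefore not evidence that no extra PD medication was needed. This rests on the medication rules alone. The range of about +5 to +43 mg/day rests on the assumed 1 to 3 of 21 participants and 100 to 300 mg/day, and only illustrates how small or cancellable the mean can be.

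The LOCF point is secondary. A week-12 value may carry a score taken at a ceiling of 15 to 50 mg/day, depending on visit and scale, against 60 at week 12. No size or direction of bias is claimed.

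The primary outcome and its decision rule are not affected. The first change should be made; the second is desirable.

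**What to change.** **LED and need for PD medication.** Reconcile the LED outcome with the medication rules; no change to those rules is proposed. In section 13.2:

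- Report per arm, with an exact 95% interval, the number of participants whose PD medication was increased or who stopped study drug because an increase was needed, including those who later restarted.
- Keep LED change as description, shown by on-drug and off-drug status.
- Repair the motor sentence and state how LED is analysed.

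The sources exist: concomitant medications (5.4.1), treatment and dosing changes for adverse events (5.4.7, 9.3), withdrawal reasons (5.2.6, 7.0) and the dispensing and return log (8.4). Check that the case report form captures the reason when someone stops study drug for something other than an adverse event but stays in the study.

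**Missing scores, a lesser change.**

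- For HAM-A, HADS and UDysRS, use a baseline-adjusted repeated-measures model on all observed visits (weeks 2, 4, 8 and 12, plus 6 and 10 for HAM-A). Report change per arm with a 95% interval.
- Count missing week-12 responder, CGI-I and PGI-I results as non-response.
- State the missing-at-random assumption, keep LOCF as a sensitivity analysis, and say whether these rules cover MDS-UPDRS motor.

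**Cost.** Revised analysis wording and slightly more analysis, with no new assessments. The model may mislead if people leave for intolerability, and missing HAM-A data would be handled differently for the mean and for the responder rate. With 5 or 6 on placebo, estimates in that arm will be imprecise.

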## 1. PURPOSE OF THE STUDY AND BACKGROUND

### 1.1. Purpose of the study

Anxiety is common in patients with Parkinson's disease (PD) and negatively impacts quality of life. Despite this, anxiety is under-treated and there have been no clinical trials specifically examining the pharmacological treatment of anxiety in PD. Buspirone may be effective for the treatment of anxiety in PD. While it has the additional potential benefit of reducing levodopa-induced dyskinesias there have also been concerns that it may worsen PD motor function. The primary objective of this study is to determine the tolerability of buspirone for the treatment of anxiety in Parkinson's disease (PD).

Primary Objective:

To determine the tolerability of buspirone in PD as defined by the proportion of participants who complete the 12-week study on study drug.

Secondary Objectives:

- a. To explore the preliminary efficacy of buspirone in reducing symptoms of anxiety.
- b. To explore the preliminary efficacy of buspirone in reducing levodopa-induced dyskinesias.
- c. To pilot the Parkinson Anxiety Scale (PAS) for assessing change in symptoms of anxiety over time.

### 1.2. Background

The prevalence of anxiety disorders in Parkinson's disease (PD) is 25%-43% and anxiety as a symptom is reported by 56% of PD patients. Anxiety negatively impacts quality of life and may be a more important determinant than depression or apathy. Yet anxiety disorders are untreated in up to 50% of patients with PD. The current state of treatment may reflect the heterogeneous phenomenology of anxiety in PD, the lack to date of an appropriate scale to detect anxiety in PD, the absence of guidelines regarding the treatment of anxiety in PD or a combination of these factors.

The National Institute of Neurological Disorders and Stroke (NINDS) 2014 PD Research Recommendations highlighted the treatment of non-motor symptoms as an area of importance. There is emerging interest in the treatment of anxiety specifically, including a recent pilot study examining the feasibility of cognitive behavioral therapy. However, there have been no clinical trials designed to evaluate the optimal pharmacological treatment of anxiety in PD. With no evidence upon which to base treatment decisions for this common and disabling condition in patients with PD, clinicians most commonly prescribe selective serotonin reuptake inhibitors (SSRIs) and benzodiazepines. However, in the multicenter Study of Antidepressants in Parkinson's Disease (SAD-PD) trial both paroxetine (an SSRI) and venlafaxine XR (a serotonin norepinephrine reuptake inhibitor or SNRI) were more effective than placebo for the treatment of depressive symptoms but neither demonstrated any effect on a secondary anxiety measure. In fact, higher baseline anxiety levels predicted poorer response to treatment of depressive symptoms. A second randomized placebo-controlled trial comparing nortriptyline and paroxetine for the treatment of

depression in PD also demonstrated no effect for paroxetine on a secondary anxiety measure. Although neither of these studies was powered to detect changes in anxiety, they highlight the need to further evaluate treatment approaches for anxiety in PD. Benzodiazepine therapy is not ideal given a side effect profile including sedation, delirium, and balance impairment associated with an increased risk of falls. Benzodiazepines are also associated with high abuse potential and there is a possible increased risk of Alzheimer's dementia associated with long-term use.

Buspirone is FDA approved for the treatment of generalized anxiety disorder. It may be possible to reposition buspirone for the treatment of anxiety in PD however it has not yet been evaluated in this population, where the pathophysiology of anxiety might be different, and it is necessary to ensure that it does not worsen PD motor function. Buspirone is primarily a 5HT1A receptor partial agonist with weak dopamine D2 and 5HT2 receptor activity. Buspirone is effective for the treatment of generalized anxiety disorder, is well-tolerated in the elderly population, and can be used as an adjunctive agent for the treatment of depression. Through its action on the 5HT1A receptor, buspirone may have the added benefit of diminishing levodopa-induced dyskinesias an effect corroborated by early clinical studies. This is a particularly compelling indication given the relationship between anxiety, motor fluctuations, and freezing of gait. However, this effect has not been conclusively demonstrated having only been shown in two very small trials and buspirone, through its effects on the dopaminergic system and weak affinity for D2 receptors, could potentially be associated with worsening of PD motor function. The potential motor impact of buspirone in PD makes a preliminary tolerability study the first logical step prior to embarking on a larger efficacy trial.

The underlying pathophysiology of anxiety in PD has not been fully elucidated and may differ from that of anxiety in the general population. Anxiety symptoms in PD can respond to treatment with dopamine agonists and, among fluctuators, anxiety may improve acutely with levodopa infusions; however, in general, anxiety does not respond well to dopaminergic treatment supporting the notion that dopamine dysregulation is not the sole pathophysiologic mechanism. Serotonergic dysfunction contributes to the pathophysiology of anxiety in the general population and 5HT1A receptors have been specifically implicated. 5HT1A receptors modify serotonergic, glutaminergic, and dopaminergic transmission and in PD, 5HT1A receptor levels are altered. In rats with anxiety-like behavior induced by 6-hydroxydopamine lesions of the medial forebrain bundle, injection of a 5-HT1A receptor agonist, 8-OD-DPAT, into the prelimbic region or medial subdivision of the central nucleus of the amygdala has an anxiolytic effect. Thus, buspirone, which is primarily a 5HT1A receptor partial agonist, is a promising therapeutic for anxiety in PD.

The phenomenology of anxiety in PD is heterogeneous. Recent studies report variable prevalence rates for anxiety subtypes in PD: generalized anxiety disorder 3-20.6%, agoraphobia without panic 1.6-15.5%, panic disorder 3.9-30%, social phobia 7.9-13%, obsessive compulsive disorder 0.8-5.5%, and anxiety disorder not otherwise specified 11.4-25%. Commonly used anxiety scales, including the Beck Anxiety Inventory, Hamilton Anxiety Rating Scale, and Hospital Anxiety and Depression Scale were developed for use in the general population and do not have ideal psychometric properties for use in PD. A new scale, the Parkinson Anxiety Scale, was developed specifically for use in the PD population and has thus far demonstrated

validity and reliability but its sensitivity to change has not yet been demonstrated. This clinical trial will pilot the use of the Parkinson Anxiety Scale for detecting change over time and determine the feasibility of using it in larger phase III trials.

